4.1.2.1 Rationale for Selection of the Primary Effectiveness Endpoint

4.2 Secondary Endpoints

Type I error among secondary endpoints will be controlled using appropriate statistical methodology as outlined in the Statistical Analysis Plan.

- 1) Proportion of subjects who achieve acute procedural success  for subjects who had the investigational catheter inserted into their vasculature, where acute procedural success is defined as confirmation of entrance block in all pulmonary veins.
- 2) Proportion of subjects off all AADs taken to treat AF/AFL/AT who achieve 15-month success of , defined as freedom from documented AF/AFL/AT recurrence (episodes >30 seconds) during the 9-month period following the blanking and therapy consolidation periods.
- 3) Proportion of subjects who achieve 15-month single procedure success of , defined as freedom from documented AF/AFL/AT recurrence (episodes >30 seconds) during the 9-month period following the blanking and therapy consolidation periods after a single ablation procedure. Any repeat ablation procedure required by the subject at any time will be deemed an effectiveness failure in this analysis.

4.3 Additional Data

Additional data to be collected in this clinical investigation are described and will be reported using summary statistics. No hypothesis tests will be performed.

- 1) Procedure- and/or ablation catheter-related adverse events throughout the 15-month follow-up period
 - 2) Success (defined as freedom from >30 second documented episodes of AF/AFL/AT recurrence) without Class I or III AAD dose increase from the historic maximum ineffective dose (prior to the ablation procedure) or initiation of a new Class I or III AAD for arrhythmia recurrence after the blanking and therapy consolidation periods.
- 

- 3) Proportion of subjects who achieve 15-month symptomatic single procedure success (defined as freedom from >30 second documented symptomatic episodes of AF/AFL/AT recurrence after the blanking and therapy consolidation periods).
- 4) Cardiovascular-related health care utilization through 15-months after the initial procedure.
- 5) Procedure data, including but not limited to, ablation data, mapping data, and usage of Automark.
- 6) Proportion of cases achieving $\geq 90\%$ lesions with $\geq 10g$ of contact force.
- 7) Evaluation of procedure data to determine target lesion index (LSI) value(s) as assessed by AF/AFL/AT recurrence.
- 8) Changes in EQ-5D-5L and AFEQT scores from baseline to follow up at 3, 6, 12, and 15-months after the initial procedure.

5 SUBJECT SELECTION AND WITHDRAWAL

5.1 Subject Population

This clinical investigation will enroll male and female subjects who have drug refractory, symptomatic, persistent AF. Subjects must provide written informed consent prior to conducting any investigation-specific procedures not considered standard of care.

5.2 Subject Screening and Informed Consent

5.2.1 Subject Screening

Members of the site's clinical investigation team (physician and/or research coordinator, or other delegated and qualified personnel) previously trained to this CIP must screen potential patients for clinical investigation eligibility and document the screening effort onto a site-specific Screening Log. Patients who meet the inclusion criteria and none of the exclusion criteria may participate in this clinical investigation.

Patients presenting at clinical sites as potential subjects will be fully informed about the clinical investigation. Once a duly dated and signed Informed Consent form is obtained, the clinical investigation-specific screening procedures may begin.

The following assessments may need to be performed after obtaining consent and prior to the procedure, as part of the screening process (further described in **Section 6**):

- Verification that a left atrial thrombus is not present on the day of or within one day of the ablation procedure
- Measurements for LVEF and LAD, if not documented prior to consent and/or is not standard of care at the site
- Administration of a 24-hour Holter, if not previously documented as part of standard of care within 90-days of the ablation procedure

Subject data will be collected following enrollment (consent) into the clinical investigation.

In the case in which a subject does not meet all inclusion criteria or meets one or more exclusion criteria that is discovered prior to insertion of the TactiCath SE catheter into their vasculature, the subject is considered a screen failure. The Principal Investigator or the delegated clinical investigation personnel will record the screen failure in the hospital records and on the Screening Log.

5.2.2 Informed Consent

A template informed consent form will be provided to each site by the Sponsor under separate cover for use in this clinical investigation. Site-specific language will be added to the template and approved by research personnel, the Sponsor, and governing IRB/EC prior for use in the trial.

The Investigator or his/her authorized designee will conduct the Informed Consent process, as required by applicable regulations and the center's IRB/EC. This process will include a verbal discussion with the subject on all aspects of the clinical investigation that are relevant to the subject's decision to participate, such as details of clinical investigation procedures, anticipated benefits, and potential risks of clinical investigation participation. Subjects must be informed about their right to withdraw from the clinical investigation at any time and for any reason without sanction, penalty or loss of benefits to which the subject is otherwise entitled. Withdrawal from the clinical investigation will not jeopardize their future medical care or relationship with the investigator.

During the discussion, the Principal Investigator or his/her authorized designee will avoid any improper influence on the subject and will respect subject's legal rights. The subject shall be provided with the Informed Consent form written in a language that is understandable to the subject and has been approved by the center's IRB/EC. The subject shall have adequate time to review, ask questions and consider participation. The Principal Investigator or his/her authorized designee will make every effort to ensure that the subject understands the information provided. If the subject agrees to participate, the Informed Consent form must be signed and dated by the subject and thereafter by the person obtaining the consent prior to any clinical investigation-specific procedures. The signed original will be filed in the subject's hospital or research charts, and a copy will be provided to the subject.

Failure to obtain informed consent from a subject prior to undergoing study-specific procedure should be reported to the Sponsor within 5 working days and to the reviewing center's IRB/EC according to the IRB's/ EC's reporting requirements.

If, during the clinical investigation, new information becomes available that can significantly affect a subject's future health and medical care, the Principal Investigator or his/her authorized designee will provide this information to the subject. If relevant, the subject will be asked to confirm their continuing informed consent in writing.

5.2.2.1 Special Circumstances for Informed Consent

The following individual populations will be excluded from participation in this clinical investigation:

- Individuals persons who are mentally ill, mentally handicapped, or individuals without legal authority, are excluded from the study population.
- Individuals under the age of 18 or age of legal consent are excluded from the study population.
- Individuals unable to read or write are excluded from the study population.
- Pregnant or breastfeeding women are excluded from the study population.

5.2.3 HIPAA Authorization Requirement (United States only)

An authorization for use and disclosure of the subject's protected health information, in accordance with the Health Insurance Portability and Accountability Act (HIPAA), must be obtained from the subject or their legally authorized representative for sites located in the United States.

5.3 Eligibility Criteria

Assessment of eligibility criteria is based on review of candidate medical records at the site, an interview with a candidate patient, and determination by the investigator. The specific tests noted in **Section 5.2.1** (24-hour Holter, LVEF, LAD, and presence of thrombus) may not be able to be completed prior to obtaining consent if they were not performed as part of standard of care. In the case where these tests were not performed as part of standard of care and are only being performed for the purposes of this study, they must be assessed after obtaining consent, but before the subject has an ablation catheter inserted into their vasculature for an ablation procedure.

Patients must meet ALL of the inclusion criteria to be considered for this clinical investigation. If ANY of the exclusion criteria are met, the patient is excluded from the clinical investigation.

5.3.1 Inclusion Criteria

- 1) Patient must provide written informed consent prior to any clinical investigation related procedure.
- 2) Documented symptomatic persistent AF, which is defined as continuous AF sustained beyond 7-days and less than 1-year that is documented by (1) a physician's note AND (2) a 24-hour Holter within 90-days prior to the procedure, showing continuous AF, OR (3) two electrocardiograms (from any form of rhythm monitoring) showing continuous AF, with electrocardiograms taken at least 7 days apart
- 3) Refractory or intolerant to at least one Class I or III antiarrhythmic drug (AAD) as evidenced by recurrent symptomatic AF
- 4) Age 18 years or older
- 5) Able and willing to comply with all pre-, post-, and follow-up testing and requirements

5.3.2 Exclusion Criteria

- 1) Continuous AF > 12 months (longstanding persistent AF)
- 2) Previous left atrial surgical or catheter ablation for atrial fibrillation or a previous procedure that required an incision in the left atrium with resulting scar
- 3) Any cardiac procedure (surgical or percutaneous) within 90-days prior to the initial procedure
NOTE: Diagnostic cardiac procedures in which no intervention, implant, or incision was made in the cardiac tissue are not considered a surgical or percutaneous cardiac procedure.
- 4) CABG surgery within the 6-months (180-days) prior to the initial procedure

- 5) Valvular cardiac surgical/percutaneous procedure (i.e. ventriculotomy, valve repair or replacement and/or presence of a prosthetic or mechanical valve)
- 6) Any carotid stenting or endarterectomy
- 7) Documented or known left atrial thrombus on imaging
- 8) Left atrial diameter > 50 mm (parasternal long axis view or by CT)
- 9) Left ventricular ejection fraction < 40%
- 10) Unable to take anticoagulation medication due to contraindication or intolerance
- 11) History of blood clotting or bleeding abnormalities
- 12) Myocardial infarction (MI), acute coronary syndrome, percutaneous coronary intervention (PCI) within the 3-months (90-days) prior to the initial procedure
- 13) Documented thromboembolic event (including TIA) within the 12-months (365 days) prior to the initial procedure
- 14) Rheumatic heart disease
- 15) Uncontrolled heart failure or NYHA functional class III or IV
- 16) Severe mitral regurgitation (regurgitant volume \geq 60 mL/beat, regurgitant fraction \geq 50%, and/or effective regurgitant orifice area \geq 0.40cm²)
- 17) Awaiting cardiac transplantation or other cardiac surgery within the 12-months (365 days) following the initial ablation procedure
- 18) Unstable angina at the time of the initial procedure
- 19) Acute illness or active systemic infection or sepsis
- 20) AF secondary to electrolyte imbalance, thyroid disease, acute alcohol intoxication, major surgical procedure in the preceding 3-months, or other reversible or non-cardiac cause
- 21) Diagnosed atrial myxoma
- 22) Presence of implanted implantable cardioverter defibrillator (ICD) or cardiac resynchronization therapy-defibrillator (CRT-D)
- 23) Significant pulmonary disease, (e.g., restrictive pulmonary disease, constrictive or chronic obstructive pulmonary disease) or any other disease or malfunction of the lungs or respiratory system that produces chronic symptoms
- 24) Significant congenital anomaly or other anatomic or comorbid medical problem that in the opinion of the investigator would preclude enrollment in this study or compliance with the follow-up requirements or impact the scientific soundness of the clinical trial results
- 25) Pregnant or nursing subjects and those who plan pregnancy during the clinical investigation follow-up period
- 26) Enrollment in an investigational study evaluating another device, biologic, or drug that may interfere with this clinical investigation at the time of the initial procedure or within 30 days prior to the initial procedure
- 27) Presence of any condition that precludes appropriate vascular access or manipulation of catheter
- 28) Life expectancy less than 12-months
- 29) Body mass index > 40 kg/m²
- 30) Known sensitivity to contrast media (if needed during the procedure) that cannot be controlled with pre-medication

- 31) Renal failure requiring dialysis
- 32) Presence of other medical, social, or psychological conditions that, in the investigator's opinion, could limit the subject's ability to participate in the clinical investigation or to comply with follow-up requirements, or impact the scientific soundness of the clinical investigation results
- 33) History of atriotomy or ventriotomy
- 34) Implanted endocardial left atrial appendage occlusion device

5.4 Subject Enrollment

A patient is considered enrolled in the clinical investigation from the moment the patient provides written informed consent and meets all eligibility criteria.

If a TactiCath SE device is used for ablation on an enrolled subject who does not meet eligibility criteria for the trial, they will not be withdrawn from the trial and will be counted in the analysis population and will complete all follow-up requirements.

5.4.1 Enrollment of Medicare Beneficiaries (United States only)

This clinical investigation will enroll Medicare beneficiaries that qualify based on the inclusion and exclusion criteria defined for this trial. This IDE clinical trial conforms to all standards of Medicare coverage requirements. The Risks and Benefits section (**Section 15**) describes how all enrolled subjects, including Medicare beneficiaries, may be affected by the device under investigation.

Subjects enrolled in this clinical investigation are expected to be consistent with the Medicare population based on demographic characteristics and cardiovascular risk factors and as such, the clinical investigation results are expected to be generalizable to the Medicare population.

5.4.2 Historically Under-Represented Demographic Subgroups

The Sponsor intends to implement FDA's guidance on sex-specific data in medical device clinical investigations to ensure adequate representation of women and other traditionally under-represented demographic subgroups in this clinical investigation. As noted in the FDA guidance, some barriers to participation of women and ethnic minorities in clinical investigations have traditionally been:

- Lack of understanding about main obstacles to participation of such subgroups in clinical research
- Inclusion/exclusion criteria potentially not needed to define the clinical investigation population may unintentionally exclude specific subgroups
- Under diagnosis of disease etiologies and pathophysiology leading to under referral of demographic subgroups
- Avoidance of specific subgroups by investigators and Sponsors due to the perception that it takes more time and resources to recruit them
- Fear of fetal consequences (for female participants)
- Family responsibilities limiting women's ability to commit time for follow-up requirements

The Sponsor will take the following steps to ensure adequate representation of women and racial or ethnic minorities in this clinical investigation:

- Abbott will provide training to investigational site personnel to ensure adequate representation of these demographic subgroups
- Abbott will approach sites without bias or consideration for specific demographic subgroups
- Abbott will have informed consent materials in alternative languages and will work with sites and IRBs/ECs on recruitment materials

5.5 Subject Withdrawal

Each enrolled subject shall remain in the clinical investigation until completion of the required follow-up period. However, a subject's participation in any clinical investigation is voluntary and the subject has the right to withdraw at any time without penalty or loss of benefit.

Abbott must be notified of the reason(s) for subject discontinuation. The site will provide this information to Abbott as documented on the appropriate CRF. Investigators must also report this to their respective IRB/EC as defined by their institution's procedure(s).

No additional follow-up will be required or data recorded from subjects once they are withdrawn from the clinical investigation. If a subject withdraws from the investigation due to problems related to the safety or performance of the device under investigation, they will be followed by their regular physician per their standard of care.

If for any reason, the subject has the TactiCath SE inserted into their vasculature, but no ablation is performed and the subject will not be rescheduled to receive another ablation procedure, the subject will be followed for 30-days to assess safety and then exited from the trial.

In the event that a subject does elect to withdraw from the trial, the site should make attempts to schedule the subject for a final visit. At this final follow-up visit, the subject will undergo assessments as outlined for an unscheduled visit (**Section 6.6.2**), if the visit does not coincide with a scheduled follow-up visit.

Withdrawn subjects count towards the total enrollment at the site and will not be replaced by enrolling additional subjects.

Lost-to-Follow-up

If the subject misses two consecutive scheduled follow-up time points and the attempts at contacting the subject (detailed below) are unsuccessful, then the subject is considered lost-to-follow-up. Site personnel shall make all reasonable efforts to locate and communicate with the subject and document their efforts, including the following, for each time an attempt was made to contact the subject:

- A minimum of two telephone calls on different days over the specified follow-up windows to contact the subject should be recorded in the source documentation, including date, time and initials of site personnel trying to make contact.
- If these attempts are unsuccessful, a letter should be sent via registered mail to the subject.
- If a subject misses one or more non-consecutive follow-up contact time points, it will be considered a missed visit. The subject may then return for subsequent visits.

- If the subject misses two consecutive time points and the above-mentioned attempts at communicating with the subject are unsuccessful, the subject will be considered lost-to-follow-up.

Note: Telephone contact with the general practitioner, cardiologist not participating in this clinical investigation, or relative without the presence of the subject or indirect documentation obtained via discharge letters will not be considered as contact with the subject.

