4.1 Primary Endpoint

4.1.1 Primary Safety Endpoint

The primary safety endpoint is the rate of device and/or procedure-related serious adverse events with onset within 7-days of any ablation procedure that uses the TactiCath SE catheter (initial or repeat procedure performed ≤ 180 days of initial procedure) that are defined below:

- Atrioesophageal fistula¹
- Cardiac tamponade/perforation¹
- Death
- Heart block
- Myocardial infarction (MI)
- Pericarditis²
- Phrenic nerve injury resulting in diaphragmatic paralysis
- Pneumothorax
- Pulmonary edema (respiratory insufficiency)
- Pulmonary vein stenosis¹
- Stroke/cerebrovascular accident (CVA)
- Thromboembolism
- Transient ischemic attack
- Vascular access complications (including major bleeding events³)

-
1. Atrioesophageal fistula, cardiac tamponade/perforation and pulmonary vein stenosis will be evaluated through 15-months.
 2. Pericarditis is a common occurrence for almost all procedures and will only be considered a primary safety endpoint event if the pericarditis pleuritic symptoms last longer than 7-days and/or requires hospitalization of greater than 24 hours for reasons other than for observational purposes only.
 3. Bleeding is a major complication of AF ablation if it requires and/or is treated with transfusion or results in a 20% or greater fall in hematocrit.

Definitions regarding the primary safety events are provided in **Appendix III**.

Serious AF/atrial flutter (AFL)/atrial tachycardia (AT) recurrences without coexisting conditions (e.g. thromboembolism, worsening heart failure, etc.) will be counted as effectiveness failures but will not count against the primary safety endpoint.

The performance goal is set at [REDACTED] as determined by relevant studies for persistent AF that utilize radiofrequency ablation. Refer to the Statistical Analysis Plan for details regarding the rationale for the performance goal.

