7.3 Adverse Event and Device Deficiency/Device Malfunction Reporting

7.3.1 Adverse Event Reporting

Safety surveillance and reporting starts as soon as the patient is enrolled in the clinical investigation. Adverse event data, including deaths, will be collected starting at the time of enrollment (after consent and eligibility criteria are met) and throughout the 15-month follow-up period and will be reported to the Sponsor on the Adverse Event CRF. Safety surveillance and reporting will continue until the last follow-up visit has been performed, the subject is deceased, the subject concludes participation in the clinical investigation or the subject withdraws from the clinical investigation.

For the purposes of this clinical investigation, the following adverse events will be reported:

- Adverse events that are assessed by the investigator as being related to either the ablation catheter or the ablation procedure will be reported in the database, preferably within 7-days of the site learning of the event
- Serious adverse events, regardless of relatedness to the procedure and/or the ablation catheter will be reported as described in **Section 7.3.2**.

Recurrence of AF, AFL, or AT are not considered reportable adverse events unless they occur in severity, frequency, or other manner that is significantly worse than the subject’s baseline condition. Recurrence of AF, AFL, or AT will affect the primary effectiveness endpoint and should be reported on the Follow-Up Visit CRF.

Additionally, urinary tract infections (UTIs) that occur after a procedure and do not require a Foley catheter will not be considered adverse events. UTIs that require a Foley catheter will be reported as AEs if related to the procedure or meet serious criteria.

Unchanged, chronic, non-worsening or pre-existing conditions are not AEs and should not be reported.

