8.2.2.3 Secondary Endpoint - Asymptomatic and Symptomatic Single Procedure Success

The hypothesis is stated as follows:

[REDACTED]

[REDACTED]

[REDACTED]

[REDACTED]

[REDACTED]

[REDACTED]

[REDACTED]

[REDACTED]

power to reject the null hypothesis with a performance goal of 16.8% and an attrition rate of 20%, is 224

[REDACTED]

[REDACTED]

[REDACTED]

[REDACTED]

[REDACTED]

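### Safety recording ends at withdrawal, with no exception for device-safety withdrawals, although three primary safety components count through 15 months

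*Protocol*

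**What the plan says.** CIP 5.5 sets a general rule for withdrawn subjects: "No additional follow-up will be required or data recorded from subjects once they are withdrawn from the clinical investigation". The next sentence takes up the subject who withdraws because of a problem with the safety or performance of the device, and says of such subjects that "they will be followed by their regular physician per their standard of care". It describes no return of information to the trial.

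CIP 7.3.1 lists the points at which safety surveillance stops. Besides the last follow-up visit and death, they are when "the subject concludes participation in the clinical investigation or the subject withdraws from the clinical investigation". SAP 3.2 repeats this.

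CIP 4.1.1 lists 14 components of the primary safety endpoint. The general window is events "with onset within 7-days of any ablation procedure that uses the TactiCath SE catheter". Three components have a longer one: "Atrioesophageal fistula, cardiac tamponade/perforation and pulmonary vein stenosis will be evaluated through 15-months".

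Two provisions soften the rule. On withdrawal, CIP 5.5 says "the site should make attempts to schedule the subject for a final visit", with the unscheduled-visit assessments of 6.6.2, which include adverse events. CIP 7.3.1 and 7.3.2 also make related adverse events and all serious adverse events reportable while the subject is still in the trial, the serious ones within 3 calendar days.

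**The concern.** The endpoint needs ascertainment to month 15 for three components, and the withdrawal rule switches it off for anyone who leaves earlier. Detection of pulmonary vein stenosis depends on contact: under CIP 6.6, imaging or an investigator visit follows when the subject reports symptoms at a scheduled visit or call. A withdrawn subject has no such contact. If the regular physician later makes the diagnosis, nothing asks the site to record it or the Clinical Events Committee (CEC) to adjudicate it.

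The loss runs in one direction for event counts: a late event can be missed but not added. Where the reason for leaving is itself a device problem, the missingness may also be informative. What is at stake is a possible downward bias in a primary safety rate tested against a fixed goal, and the completeness of the record on rare, severe complications in a pre-market submission.

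**Working it through.** **Inputs.** N = 224, goal 16.8% and attrition 20%, from the legible fragment of the sample-size text after CIP 8.2.2.3: "power to reject the null hypothesis with a performance goal of 16.8% and an attrition rate of 20%, is 224". Under CIP 5.5, "Withdrawn subjects count towards the total enrollment at the site and will not be replaced by enrolling additional subjects". Alpha, power and the expected event rate are redacted, so the sample size itself cannot be reproduced. I assume a one-sided exact binomial test at 0.05 and at 0.025.

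**Attrition step.** 179 / (1 - 0.20) = 223.75, which rounds up to 224, so the inflation is coherent. It leaves 224 x 0.20 = 44.8, or about 45 subjects, without complete follow-up. The 20% is not split by cause, so 45 also includes loss to follow-up and is an upper bound on withdrawals.

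**Passing limits.** These are the largest k with P(X <= k | n, 0.168) <= alpha.

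| n | alpha 0.05 | alpha 0.025 |
|---|---|---|
| 179 | 21 (11.7%) | 20 (11.2%) |
| 224 | 28 (12.5%) | 26 (11.6%) |

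**Missed events needed to reverse a pass.** This depends on how withdrawn subjects enter the analysis, and that rule is redacted.

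- Kept in the denominator of 224 as event-free: a result exactly at the limit (28 or 26) fails with one more event.
- Left out, then restored: a result at the limit of 179 has room for 28 - 21 = 7 or 26 - 20 = 6 events among the 45. The 8th or 7th reverses it.
- Away from the limit, with an assumed 12 events in 179: there is room for 28 - 12 = 16 or 26 - 12 = 14, so 17 or 15 events among 45 would be needed.

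**Chance of missing something.** Let r be the late-event rate after withdrawal. The documents give no figure, so r is assumed. Expected missed events are 44.8 x r. The chance of at least one among 45 is 1 - (1 - r)^45. If withdrawn subjects count as event-free, the rate over 224 is understated by 0.20 x r.

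| r | Expected missed | P(at least one) | Understatement |
|---|---|---|---|
| 1% | 0.45 | 36% | 0.2 points |
| 2% | 0.90 | 60% | 0.4 points |
| 5% | 2.24 | 90% | 1.0 point |

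If only 10% withdraw (about 22 subjects), the expected counts and understatement halve and the chances become 20%, 36% and 68%.

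**A related mismatch.** CIP 4.1.1 evaluates tamponade/perforation through 15 months, while the CEC definition in Appendix III confines it to the procedure and the 30 days after it. Until these are reconciled, the late window may in effect cover two components or three.

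**The case against.** The strongest reply is that the gap is narrow. Eleven of the 14 components close 7 days after an ablation. A qualifying event that prompts withdrawal has by then occurred and is reportable. The reason for withdrawal goes to the sponsor on a case report form, and a final visit is to be attempted. All of this stands, and it limits the gap to events first diagnosed after the last contact. It does not close it: the site need only attempt the visit, 6.6.2 does not list vein imaging, and nothing reaches past that visit.

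Three stronger readings are tempting and unsupported.

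- A reader might infer that 5.5 expressly stops data collection for device-safety withdrawals. It does not. It states a general rule and then says who provides care; the supportable statement is that no exception is made.
- A reader might infer that late events are lost in the very subjects most likely to have them. That is plausible, but no figure in the documents shows it.
- A reader might infer that one or two unrecorded events would overturn a borderline result. That holds only if withdrawn subjects stay in the denominator as event-free.

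Missing-data sensitivity analyses are promised in CIP 3.2, and their content (SAP 2.9 and 2.13.1) is redacted. They may well bound the effect, and I make no criticism of text I cannot see. Bounding is still not the same as having the event. The consent template is a separate document, so its data-use terms are also unknown.

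**Conclusion.** The point holds as a gap in ascertainment. Recording and surveillance stop at withdrawal in three concordant places, device-safety withdrawals are not exempted, and three primary safety components are nominally counted to month 15. Apart from pre-withdrawal reporting and an attempted final visit, later events in these subjects are not captured, and the safety rate can be biased downward.

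The effect on the formal test is probably small: it matters only if the observed rate is near 11-12%. Even there, a single missed event decides the result only under the event-free convention; otherwise 8 (alpha 0.05) or 7 (alpha 0.025) are needed. This rests on the assumed alpha, an exact test, and 45 as an upper bound. The case for change rests more on the chance of missing at least one severe event, 36% to 90% over assumed rates of 1% to 5%. The plan should be amended, but the gap does not by itself put the primary conclusion in doubt.

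**What to change.** In CIP 5.5, separate stopping study visits from withdrawing consent to data use. Suggested text: *A subject may stop study visits and still allow limited data collection. Unless the subject refuses, the site will collect vital status, atrioesophageal fistula, cardiac tamponade/perforation and pulmonary vein stenosis through month 15 by record review or contact with the regular physician. Any such event, and any safety event that led to withdrawal, will be sent to the CEC.*

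Amend the end-of-surveillance sentences in CIP 7.3.1 and SAP 3.2, and the consent template, to match. State that the note in 5.5 on contact with other physicians and discharge letters governs only the lost-to-follow-up definition, so that it does not block this collection. Reconcile the tamponade/perforation window in 4.1.1 with the definition in Appendix III.

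The cost is wording in the CIP, SAP and consent form, and modest site time for record checks, with no added procedure or visit. The observed safety rate may come out slightly higher. The change does nothing for subjects lost to follow-up.
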